Honey has a rich history of utilisation dating back to ancient times, thanks to its nutritional and therapeutic properties [21]. Honey is produced globally and is primarily composed of carbohydrates, particularly in the form of monosaccharides like fructose and glucose. Honey is enriched with different biological compounds, like flavonoids and other types of antioxidants, which have been suggested to have cardioprotective benefits [22]. It has a lower glycemic index compared to regular sugar, which may result in a slower release of glucose into the bloodstream and potentially have a favourable impact on blood sugar levels [23].

Coffee and tea are either taken plain or sweetened with sugars, such as white sugar or artificial sweeteners. However, the use of natural sweeteners like honey is becoming more and more popular. Research on the possible health impacts of coffee, tea, and honey has been done separately; nevertheless, a significant gap persists in the research regarding the synergistic effects of tea and coffee when sweetened with honey. This study will investigate whether a three-day consumption of coffee and tea sweetened with honey will significantly influence the blood pressure and blood glucose level in healthy young female adults.

Study goals and objectives

Goals

The primary aim of this study is to determine the effect of acute consumption of honey-sweetened coffee, black tea, and green tea on systolic blood pressure, diastolic blood pressure, heart rate, and blood glucose level in healthy female participants.

Objectives

- To determine whether a three-day consumption of honey-sweetened black tea, green tea, and coffee will have an effect on blood pressure in healthy female individuals.
- To determine whether a three-day consumption of honey-sweetened black tea, green tea, and coffee will have an effect on heart rate in healthy female individuals.
- To determine whether a three-day consumption of honey-sweetened black tea, green tea, and coffee will have an effect on blood glucose level in healthy female individuals.

Study design

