The study is an experimental study; specifically, it is a randomized controlled trial that will involve healthy young female adults between the ages of 18 and 26 years. The participants will consume honey-sweetened black tea, green tea, and coffee, or plain black tea, green tea, and coffee, or warm water, one cup a day for 3 days. The study will be carried out in the Physiology Laboratory, University of Uyo, and will be done within the period of July to October 2023. Each participant will fill out a consent form prior to the study, after which the participants will be given the beverages and observed for 60 minutes, during which their blood pressure, heart rate, and blood glucose level will be measured. This procedure will be repeated for the 3 days of the study. Prior to the consumption of the beverages, baseline measurements of blood pressure, heart rate, and blood glucose will be taken. For this study, a minimum of 200 volunteers will be recruited, and out of this, the eligible participants will be selected.

Methodology

The randomized controlled trial will be carried out among female students studying at the University of Uyo. The participants will be randomly grouped as follows:

Group 1 (Control) will be given 250 mL of water.

Group 2 (Coffee group) will be given 2.25 g of coffee per 250 mL of hot water.

Group 3 (Honey-sweetened coffee group) will be given 2.25 g of coffee per 250 mL of hot water with 20 mL of honey.

Group 4 (Black tea group) will be given one tea bag (2 g) per cup (250 mL) of hot water.

Group 5 (Honey-sweetened black tea) will be given one tea bag (2 g) per cup (250 mL) of hot water with 20 mL of honey.

Group 6 (Green tea group) will be given one bag (2 g) per cup (250 mL) of hot water.

Group 7 (Honey-sweetened green tea) will be given one bag (2 g) per cup (250 mL) of hot water with 20 mL of honey.

Study procedure

• Participants will be screened for eligibility criteria and will be provided with informed consent to participate in the study.

• The participants will be divided into seven groups, as specified above, through random allocation.

• After arrival, the subjects will be allowed to rest for 30 minutes. Then, baseline measurements of their blood pressures, heart rates, and blood glucose levels will be taken. This will serve as the 0-minute measurement. The subjects will then be given the standardized drinks according to their groups.

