• Blood pressures and heart rates of the subjects will be measured and recorded 15 minutes, 30 minutes, 45 minutes, and 60 minutes after consumption of the drinks, while blood glucose levels of the subjects will be measured and recorded 30 minutes and 60 minutes after consumption.

• Blood pressure and heart rate will be measured using a digital sphygmomanometer. Blood pressure is measured in millimeters of mercury (mmHg) and recorded with the systolic number first, followed by the diastolic number. Heart rate is measured in beats per minute (bpm).

• Blood glucose level will be measured with a glucometer. Blood glucose level will be measured in mg/dL.

Intervention

Coffee, black tea, green tea, and honey

The coffee that will be used for this study is Nescafé Gold Blend, manufactured by Nestlé Coffee Brand, Nestlé Global, Vevey, Switzerland. The black tea is Lipton Yellow Label Black Tea, manufactured by Lipton Teas and Infusions, Rotterdam, Netherlands, and the green tea is Qualitea Natural Green Tea, packed by Qualitea Ceylon (PVT) LTD, Wattala, Colombo, Sri Lanka. These will be obtained from Market Square, Ibom Tropicana Mall, Uyo, Akwa-Ibom State, Nigeria. Raw dark amber honey produced by Apis mellifera adansonii will be used for this study, and it will be obtained from Vika Farms located in Mbak Etoi, Akwa-Ibom State, Nigeria.

The participants will be given a cup per day for 3 days. A tea cup will be prepared by infusing a tea bag in 250 mL of hot water (95°C for black tea and 80°C for green tea). The infusion will be done for 7-10 minutes with constant stirring. A cup of coffee will be prepared by dissolving 2.25 g of instant coffee in 250 mL of 95°C water with proper stirring.

The water will be allowed to boil and cooled down to a respectful temperature before the addition of either a tea bag or coffee. The beverages will then be allowed to cool to approximately 35 degrees before honey is added and given for consumption. The control group will be given 250 mL of water at 35°C.

Measurement of blood pressure, heart rate, blood glucose

Blood pressure and heart rate will be recorded on the left arm using an automated blood pressure monitor (Shanghai Little Doctor Electronics CO. LTD, Nantong 226007, China). First, the cuff

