will be firmly placed around the arm (biceps). Then the power button will be pressed, and the automatic machine will read the blood pressure through the cuff. The reading will be taken three times, and the average value will be determined.

Blood glucose level will be measured by the oxidase method using a fine test glucometer (Osang HealthCare (Infopia), [name]). Firstly, the fingertip will be cleaned with an alcohol wipe and allowed to dry completely. The glucometer will be turned on, and a test strip will be inserted into the designated slot. A lancing device will be used to gently prick the fingertips of the subjects. The finger will be gently squeezed to help produce a small blood drop. Then the edge of the test strip will be used to touch the blood droplet until the meter beeps or indicates that it has received enough blood. The glucometer will process the blood sample and display the blood glucose level on the screen.

Sample size

The sample size was determined to assess the number of participants required to measure the mean difference between groups. The sample size was calculated using the formula explained by Charan et al. [24].

Sample size = $[2SD^2(1.96 + 0.84)^2] \div d^2$

Where:

SD = standard deviation from previous studies or pilot study

d = effect size- difference between mean values

However, a sample size of 70 will be used in this study based on available funds, equipment, manpower, and data from the literature.

Randomized controlled trial procedures

Recruitment and screening

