To ensure protection of confidentiality, the data will be entered into the study database with no personal identity, and the source documents will refer to participants solely by their study identification number. Access to the data will be restricted to the research investigators. The study database will be securely stored in the central library of the University of Uyo and Faculty of Basic

Medical Sciences library. Additionally, all data will be compiled into a thesis that will not disclose any participant identities or information. Three copies of the thesis will be generated, which will be distributed as follows:

One copy will be submitted to the Faculty of Basic Medical Sciences library for preservation.

One copy will be retained in the Department of Physiology.

One copy will be kept in the University of Uyo library.

Ethics

All data collected during this study will be treated as strictly confidential. The personal information will be anonymized, and any published results will not include identifiable information. Participation in this study is entirely voluntary. The participants have the right to refuse to participate or withdraw from the study. The participants will consent to participate by filling out and signing an informed consent form. The protocol of this study will be submitted to the Akwa-Ibom State Health Research Ethics Committee, Ministry of Health, Akwa-Ibom State, Nigeria, for approval.

Statistical analysis

The results will be presented as mean \pm standard error of the mean (SEM). All data collected from the research will be analyzed using the Microsoft Excel (MS Excel) application and GraphPad Prism Software (Version 8.1). One-way and two-way analysis of variance (ANOVA), as well as Tukey's post-hoc comparison, will be used to determine the significant differences between the mean values. The statistical significance will be accepted at the level of P < 0.05.

Discussion

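### The ANOVA plan does not say how repeated readings from one participant are handled; if they enter a group-by-time ANOVA as independent rows, the overall group test is badly inflated

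*Combined protocol and SAP*

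**What the plan says.** The inferential plan is one sentence under Statistical analysis: "One-way and two-way analysis of variance (ANOVA), as well as Tukey's post-hoc comparison, will be used". The same section sets significance at P < 0.05, presents results as mean ± SEM, and names Excel and GraphPad Prism without a procedure or model option.

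The data to be analysed are described elsewhere in the protocol:

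- Study procedure: a reading before the drink, of which it says "This will serve as the 0-minute measurement". Blood pressure and heart rate are then "measured and recorded 15 minutes, 30 minutes, 45 minutes, and 60 minutes after consumption of the drinks". The glucose schedule is shorter, with two post-drink readings: "while blood glucose levels of the subjects will be measured and recorded 30 minutes and 60 minutes after consumption".
- Study design: "Prior to the consumption of the beverages, baseline measurements of blood pressure, heart rate, and blood glucose will be taken", and "This procedure will be repeated for the 3 days of the study".
- Randomization: the participant is the unit allocated to a group.
- Measurement of blood pressure, heart rate, blood glucose: "The reading will be taken three times, and the average value will be determined". This reduces three cuff readings at one time to one value. It is the only averaging rule in the document.

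No section states the factors of either ANOVA, whether readings are matched within participant, what the 0-minute value is used for, or what happens to day.

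**The concern.** Readings taken from one person within an hour, and again on the next two days, are very likely to be correlated. Participants were randomised, so the evidence on a beverage effect comes from 70 people, not from several hundred readings. An ANOVA that treats each reading as a separate observation judges differences between groups against an error term that is too small. A chance difference between groups of about 10 people can then be declared a beverage effect. The group-by-time test, which asks whether the response over the hour differs between drinks, is judged against an error term that is too large, so real differences can be missed.

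The design has three factors (group, time, day) and a two-way ANOVA holds two. Analysing days separately or averaging over them would both be legitimate, but the plan does not say which. It therefore does not separate the sound executions from the unsound one before results are seen.

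**Working it through.** **Inputs from the protocol.** 7 groups; 70 participants (Sample size); 5 readings per day for blood pressure and heart rate (0, 15, 30, 45, 60 min); 3 per day for glucose (0, 30, 60 min); 3 days; alpha 0.05. If the baseline is repeated daily, each person gives up to 5 × 3 = 15 or 3 × 3 = 9 values.

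**Assumptions.** Equal groups of 10 (not stated). Equal within-person correlation ρ, shown over a range because the protocol gives no SD or correlation. One day, no true effect. The plan states no error rate for this analysis beyond P < 0.05, so there is no figure of its own to reproduce.

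**Degrees of freedom.** One day has 70 × 5 = 350 rows and 7 × 5 = 35 cells, so row-level error df = 315. For glucose, 210 − 21 = 189. The participant-level test has 70 − 7 = 63.

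**Expected mean squares** (total variance 1, m readings each):

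- group: 1 + (m − 1)ρ
- group-by-time: 1 − ρ
- row-level error: {63[1 + (m − 1)ρ] + 63(m − 1)(1 − ρ)} / 63m = 1

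The row-level group F is therefore too large by the factor 1 + (m − 1)ρ, and the row-level interaction F too small by 1 − ρ.

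**Hand check, m = 5, ρ = 0.5.** The factor is 1 + 4 × 0.5 = 3.0, and the 5% critical value of F(6, 315) is 2.127. With the error mean square fixed at 1, the rejection rate is P(χ²₆ > 6 × 2.127 / 3.0) = P(χ²₆ > 4.25) ≈ 64%.

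**Simulated rejection rates, nominal 5%** (400,000 draws per setting; at ρ = 0 every test gives 5.0%):

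| Test | ρ = 0.1 | 0.2 | 0.5 | 0.7 |
|---|---|---|---|---|
| Group, rows, 5 readings | 17% | 32% | 64% | 76% |
| Group, rows, 3 readings | 10% | 17% | 38% | 50% |
| Group, rows, 4 post-drink readings | 14% | 24% | 53% | 66% |
| Group, rows, 2 post-drink readings | 7% | 10% | 20% | 28% |
| Group-by-time, rows, 5 readings | 2.0% | 0.6% | <0.1% | <0.1% |
| Group, participant means | 5% | 5% | 5% | 5% |

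Tukey on group means averaged over time follows the group test: any false pair in about 16% / 29% / 61% / 73% (5 readings) and 10% / 16% / 36% / 47% (3 readings), 20,000 runs. If correlation decays over the hour (adjacent correlation 0.1 to 0.85), the row-level group test rejects 10% to 78% (5 readings) or 8% to 55% (3 readings).

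**Tukey at a single time.** With the same row-level error term, comparing groups at one time rejects about 5% to 6% per time for ρ from 0 to 0.85. Each cell mean comes from 10 different people, and the pooled error estimates the total variance at one time.

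**Lost power for group-by-time.** Suppose the three honey arms are raised by 0.75 SD at 30 to 60 minutes (an illustrative pattern). With 5 readings, power with rows against power with within-person error is 31% against 45% at ρ = 0.1, and 4% against 78% at ρ = 0.5.

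**SEM.** Pooled over times as rows, an SEM is too small by √[1 + (m − 1)ρ]. For ρ from 0.1 to 0.7 that is about 1.2 to 1.9 (5 readings) or 1.1 to 1.5 (3 readings). SEMs by group and time are not affected.

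**The case against.** The strongest reply is that nothing in the plan prescribes independent rows. One-way ANOVA on one value per person, or at one time on one day, fits the sentence. So does a group-by-time ANOVA with participants matched across times. Both handle the correlation. A beverage-by-honey ANOVA on one value each would also do so, but only with the water control left out, because there is no honey-in-water arm. This stands: the plan is under-specified and does not state a wrong test.

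The reply also holds that the harm needs a second step, namely use of the time-averaged group test. Comparing groups at each named minute fits the wording equally well and stays near 5% per time even with rows. This stands too. Making such comparisons at several times raises the chance of any false finding (14% to 22% with 5 readings), but separate one-way ANOVAs at each time do the same (13% to 23%). That is a multiplicity question, not this one.

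The wide range of rates is fair comment: it reflects missing correlations and an assumed equal allocation. The direction needs only positive correlation. At ρ = 0.05 with 5 readings the rate is already about 10%.

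Finally, the Goals name acute consumption, while the Objectives ask "whether a three-day consumption of honey-sweetened black tea, green tea, and coffee will have an effect on blood pressure". Both are documented targets, so the remedy should not impose one of them as the main result.

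**Conclusion.** The gap is real and affects every outcome. For readings repeated within participant, the plan gives no unit of analysis, no factors, no use of the 0-minute value and no handling of day. If readings enter a group-by-time ANOVA as independent rows, the group main effect and Tukey on time-averaged means reject a true null at 17% to 76% (5 readings) or 10% to 50% (3 readings) for correlations of 0.1 to 0.7, and the group-by-time test becomes conservative and loses power. These figures rest on row-level execution, assumed correlations, 7 equal groups of 10 and a single day.

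A reader might infer that the plan prescribes an invalid test, that every between-group comparison would be inflated, or that a two-way ANOVA is wrong because the design has three factors. The documents support none of these. Sound executions fit the text, single-time comparisons stay near nominal, and separate or averaged days are legitimate once stated. Pooling all three days as rows would be worse, but no section describes it, so no figure is claimed.

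**What to change.** Replace the ANOVA sentence under Statistical analysis with a paragraph that makes the participant the unit of analysis:

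- **Group comparison.** ANCOVA on one post-drink value per participant for each outcome (for example, the mean of the post-drink readings), adjusted for the 0-minute value, with Tukey-adjusted contrasts. That is 70 values and 70 − 7 − 1 = 62 error df. Adjusted for the day-1 value, it rejected 4.9% to 5.2% under the null with equal correlation, and 4.2% to 5.7% with decaying correlation.
- **Group-by-time.** Repeated-measures ANOVA with group between and time within participant, with Greenhouse-Geisser correction. On three-day averages of the four post-drink times it rejected 4.6% to 8.2% uncorrected and 4.3% to 5.7% corrected.
- **Day.** State whether days are averaged or analysed separately.
- **Baseline.** Use the day-1 0-minute value as covariate for the three-day effect. Use the same-day value only where the same-day acute response is the stated target, because on days 2 and 3 it is measured after earlier drinks. Whether any carry-over exists is unknown.
- **SEMs.** Compute them over participants.
- **Any two-way ANOVA that is kept.** Name its factors. If they are beverage and honey, say that the water control is left out.

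A linear mixed model with a participant effect is an optional equivalent. With complete data it gave the same main group contrasts as the ANCOVA.

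The cost is one paragraph and slightly more analysis work, with no extra data or participants. The mixed model might need other software; the ANCOVA and repeated-measures ANOVA avoid it. The stated study period is July to October 2023, so if data already exist, the clarification should be dated and disclosed as made afterwards.

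### The analysis section names no ANOVA factors, comparator or analysed value for a 3 × 2 (beverage × honey) design plus water; Tukey over all seven groups would adjust each sweetened-v-plain difference for 21 pairs

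*Combined protocol and SAP*

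**What the plan says.** The Methodology section lists seven groups. Groups 2 to 7 are coffee, black tea and green tea, each plain and with a fixed volume of honey, for example "Group 3 (Honey-sweetened coffee group) will be given 2.25 g of coffee per 250 mL of hot water with 20 mL of honey". This is a complete 3 (beverage) × 2 (honey) layout. The remaining group lies outside it: "Group 1 (Control) will be given 250 mL of water".

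The Objectives ask "whether a three-day consumption of honey-sweetened black tea, green tea, and coffee will have an effect on blood pressure", and likewise for heart rate and glucose, without saying compared with what. They mention only the sweetened drinks. The abstract's discussion paragraph and the closing Discussion section put the plain drinks within the aim as well.

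Under Study procedure, blood pressure and heart rate are "measured and recorded 15 minutes, 30 minutes, 45 minutes, and 60 minutes after consumption of the drinks", and glucose at 30 and 60 minutes. Study design adds: "This procedure will be repeated for the 3 days of the study".

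The Statistical analysis section offers means with SEM, and then "One-way and two-way analysis of variance (ANOVA), as well as Tukey's post-hoc comparison, will be used to determine the significant differences" between mean values, at P < 0.05. No other section gives the factors, the comparator, the time point or day, the use of baseline, or the set of tests to which an adjustment applies.

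**The concern.** The design can isolate the effect of adding honey within each beverage, but the analysis does not say that it will. The two-way ANOVA could be beverage × honey, group × time or group × day. The comparator for a sweetened drink could be water or its own plain version, and these answer different questions. The analysed value could be any of many time-by-day readings or a summary of them.

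Two things are at stake. First, comparator, time and day can be settled after the results are known. Tukey controls error within one ANOVA, not across a series of ANOVAs on successive time points and days. Second, if seven-group Tukey carries the answer, the few comparisons that bear on honey pay for many that do not.

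**Working it through.** **Inputs.** From the documents: total sample size 70 (Sample size); seven groups (Methodology); P < 0.05 (Statistical analysis); a formula with 1.96 and 0.84, that is, two-sided 5% and 80% power for one two-group comparison (Sample size). Assumed: 10 per group (70/7; the split is not stated), one value per participant, no baseline adjustment unless noted. Differences are in units of the SD of the analysed value, because the documents give no SD.

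**The plan's own figure.** The 70 cannot be reproduced: SD and d have no values, and the text attributes 70 to funds, equipment, manpower and literature. Solved backwards at 10 per group, the formula implies d/SD = 2.8 × √(2/10) = 1.25. It has no term for multiple comparisons.

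**Pairs.** 7 × 6 / 2 = 21. These are 3 sweetened v own plain version, 3 sweetened v water, 3 plain v water, and 12 between different beverages.

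**Precision of one pair.** Pooled error df = 70 − 7 = 63; SE = √(2/10) = 0.447 SD. Power is from the noncentral t.

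| Method | Critical \|t\| | Half-width (SD) | Detectable at 80% (SD) | Power at 0.8 SD | Power at 1.25 SD |
|---|---|---|---|---|---|
| Unadjusted | 1.998 | 0.89 | 1.27 | 42% | 79% |
| Bonferroni over 3 pairs | 2.460 | 1.10 | 1.48 | 26% | 63% |
| Tukey over 7 groups | 4.307/√2 = 3.046 | 1.36 | 1.75 | 12% | 41% |

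Half-width = critical value × 0.447. Planned pairs are narrower by 1 − 2.460/3.046 = 19%.

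**Baseline adjustment.** Factor √(1 − r²). At an assumed baseline correlation r of 0.5 it is 0.866: planned pair 1.48 × 0.866 = 1.28 SD, Tukey pair 1.51 SD. At r = 0.7 it is 0.714: 1.06 and 1.25 SD.

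**Average honey effect (30 v 30).** SE = √(2/30) = 0.258 SD; unadjusted half-width 0.52 SD, detectable 0.73 SD. If honey shifts one beverage by 0.8 SD and the others not at all, the average is 0.8/3 = 0.27 SD and its power is 17%.

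**Repeated testing.** Post-drink cells: 3 outcomes × 4 times × 3 days + glucose 2 × 3 = 42; one blood-pressure outcome has 4 × 3 = 12. Simulation with no true effects (20,000 runs), seven-group Tukey in each of the 12 cells, exchangeable within-person correlation:

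| Assumed correlation | Any of the 6 sweetened-v-plain or sweetened-v-water pairs | Any of 21 pairs |
|---|---|---|
| 0.5 | 16% | 36% |
| 0.7 | 12% | 27% |
| 0.9 | 7% | 16% |

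**The case against.** **The two-way ANOVA may already be beverage × honey.** It would then yield a honey main effect and an interaction, and Tukey might cover six cells (15 pairs) rather than seven. This stands as a possibility, so the 21-pair figure is conditional. It does not remove the problem: the text does not choose, and six-group Tukey (critical value 2.954 on 54 df) still gives a half-width of 2.954 × 0.447 = 1.32 SD.

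**Twelve separate Tukey runs are not in the plan.** Correct. Time could be handled within one model. A reader might infer that the plan carries a 16-36% false-positive rate. The documents do not support that: the range needs twelve separate runs and assumed correlations, and it counts beverage-v-beverage pairs that no objective asks about. For the six pairs the range is 7-16%. It shows what the wording permits, not what will happen.

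**All-pairs Tukey is legitimate.** Within a single ANOVA it is valid. If the aim covers plain drinks too, nine of the 21 pairs are of interest (3 + 3 + 3), so a broad procedure is less wasteful than a count of three suggests. This stands, and it is why the plain-v-water pairs need an explicit status.

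**The pooled honey effect is far more precise.** A reader might infer that it should be the main test. No objective states an averaged question, and the average informs only if honey acts broadly alike across beverages. It belongs among supportive results.

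**The real limit is sample size.** Largely true. Planned contrasts improve a drink-specific pair only from 1.75 to 1.48 SD.

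**Conclusion.** The point holds in conditional form. What is certain is the omission: a 3 × 2 layout plus water control is to be analysed by unnamed ANOVAs and Tukey, with no factors, comparator, analysed value or family of tests. This is more than missing detail, because one reading is a poorer method than the design allows. Tukey over seven groups is needlessly wide for the sweetened-v-plain question (1.36 against 1.10 SD), and repeating it over time-by-day cells would not hold 5% per outcome.

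The widths rest on 10 per group and one value per participant. The false-positive ranges rest also on assumed exchangeable correlations of 0.5 to 0.9 and on separate runs per cell. The plan should be changed, but the change makes the question definite more than it makes the study powerful.

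**What to change.** In Statistical analysis:

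1. For each outcome, test one baseline-adjusted summary per participant, for example the average of post-drink values over times and days. Say which 0-minute reading is the baseline: if one is taken each day, those on days 2 and 3 follow earlier drinks. Keep any group × time analysis as supporting.
2. Make the three sweetened-v-plain differences planned contrasts with their own adjustment, for example Bonferroni over three, reported with confidence intervals. The average honey effect and the honey-by-beverage interaction may be reported as supportive, with the caveat that the average is informative only if honey acts broadly alike across beverages.
3. Treat comparisons with water as a separate named family with its own adjustment. State whether the three plain drinks are included, since the abstract and the Discussion place them in the aim. Say which family is primary: two families at 5% each can reach up to 10% jointly. Say how the four outcomes are handled. Label the remaining Tukey pairs exploratory.

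Cost: a few sentences; no added participants, visits or measurements. Downsides: the gain for drink-specific pairs is modest, power stays low (about 26% at 0.8 SD), time-course detail leaves the main test, and beverage-v-beverage pairs become exploratory. Plain-v-water pairs also become exploratory unless they are put in the water family, and including them makes that family's adjustment stricter.
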